8.4.2 SERIOUS ADVERSE EVENT REPORTING

All SAEs will be reported to the PI and Regeneron Pharmaceuticals, Inc. within 24 hours after identification and recorded in OnCore and Regeneron Pharmaceuticals, Inc. by the investigator. All deaths and immediately life-threatening events, whether related or unrelated to the study agent/procedure, will be recorded on the SAE Form and submitted to the PI and Regeneron Pharmaceuticals, Inc. within 24 hours of site awareness. All SAEs will be followed until satisfactory resolution or until the investigator deems the event to be chronic or the adherence to be stable.

The reporting to Regeneron Pharmaceuticals will be done by email, [contact].

8.4.3 UNANTICIPATED PROBLEM REPORTING

The study investigator will report to the PI unanticipated problems and it will be on the discretion of the PI whether to conduct an evaluation of an unanticipated problem and whether to report it to IRB.

8.4.4 EVENTS OF SPECIAL INTEREST

Not Applicable.

8.4.5 REPORTING OF PREGNANCY

Pregnancy when diagnosed will be reported to the PI and to the reviewing IRB as soon as possible, but in no event later than 10 working days after the investigator first learns of the effect.

8.5 STUDY HALTING RULES

Administration of study agent will be halted when 3 grade 3 AEs determined to be “probably related” are observed. The study sponsor and investigators will be notified immediately when the third grade 3 event is reported and enrollment screens will stop accepting new study participants. The Protocol Monitoring Committee (PMC) will convene an ad hoc meeting by teleconference or in writing as soon as possible. The PMC will provide recommendations for proceeding with the study to the study sponsor.

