7.8 RESCUE MEDICATIONS, TREATMENTS, AND PROCEDURES

Immuno-oncology agents are associated with AEs that can differ in severity and duration than AEs caused by other therapeutic classes. Cemiplimab-rwlc is considered an immune-oncology agent in this protocol. Early recognition and management of AEs associated with immuno-oncology agents may mitigate severe toxicity. Management Algorithms have been developed to assist investigators in assessing and managing the following groups of AEs:

- Gastrointestinal
- Renal
- Pulmonary
- Hepatic
- Endocrinopathy
- Skin
- Neurological

The above algorithms can be found in [Appendix 1](#)

Hypersensitivity infusion reactions should be reported to the site principal investigator and Regeneron Pharmaceuticals, Inc. within 24 hours of the event regardless of grade. The following AE terms constitute hypersensitivity infusion reactions:

- Allergic reaction
- Anaphylaxis
- Cytokine release syndrome
- Serum sickness
- Infusion reactions
- Infusion-like reactions

Management of infusion reactions.

Infusion reaction treatment guidelines are summarized in Table 4 below. Institutional standards for infusion reactions may be followed if the treating physician deems them acceptable for this protocol.

Table 4. Management of infusion reaction

Grade 1 Mild reaction	Increase monitoring of vital signs as medically indicated until the patient is deemed medically stable in the opinion of the investigator	None

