8.2.2 RELATIONSHIP TO STUDY AGENT

For all collected AEs, the clinician who examines and evaluates the participant will determine the AE's causality based on temporal relationship and his/her clinical judgment. The degree of certainty about causality will be graded using the categories below.

Related – The AE is known to occur with the study agent, there is a reasonable possibility that the study agent caused the AE, or there is a temporal relationship between the study agent and event. Reasonable possibility means that there is evidence to suggest a causal relationship between the study agent and the AE.

Not Related – There is not a reasonable possibility that the administration of the study agent caused the event, there is no temporal relationship between the study agent and event onset, or an alternate

etiology has been established.

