8.4 REPORTING PROCEDURES

8.4.1 ADVERSE EVENT REPORTING

All AEs occurring prior to initiation of Cemiplimab-rwlc therapy do not need to be reported.

All AEs occurring after first administration of Cemiplimab-rwlc therapy and 30 days after last administration of Cemiplimab-rwlc will be considered as on treatment. All AEs will be collected and graded according to CTCAE v5.0, with the exception of Grade 1 laboratory abnormalities which will not be collected. All Grade 2 and above toxicities will be collected and documented by the investigator, but only Grade 3 toxicities deemed possibly, probably or definitely related to the study treatment will be reported on the appropriate CRFs/SAE reporting forms. Only SAEs will be reported to the PI and Regeneron Pharmaceuticals, Inc. All AEs, including those persisting after end of study treatment must be followed up until they have resolved or have been sufficiently characterized or the principal investigator decides to not further pursue them.

Serious and non-serious AEs occurring later than 30 days after last administration of trial drugs will only be reported in case they are considered drug-related or trial (procedure) related.

Deaths (unless they are considered drug-related or trial related) will not be reported as SAE when

they occur later than 30 days after last administration of the trial.

Serious and non-serious AEs occurring after the subjects initiate subsequent treatment will only be collected if deemed related to cemiplimab-rwlc.

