8.6 SAFETY OVERSIGHT

Serious Adverse Events: Serious Adverse Events (SAEs) from this protocol will be reported concurrently to the IRB (per IRB reporting guidelines), the study sponsor via submission through The Online Collaborative Research Environment (OnCore). SAEs will also be reported to Regeneron Pharmaceuticals, Inc.

Protocol Monitoring Committee (PMC):

The PMC meets monthly and reviews accrual, patterns and frequencies of all adverse events, protocol violations and when applicable, internal audit results.

The data and safety plan will define criteria for stopping the trial according to rules set forth by this protocol. This trial will be continuously monitored by the site PI and the research team at each participating institution. All participating sites will have a monthly teleconference calls to monitor any safety concerns. Safety and monitoring reports will be submitted to the PMC after completing the first 2 cycles after the enrollment of initial 3 patients or more frequently if requested by the PMC. No additional interim analyses will be conducted. A final safety and monitoring report including all 27 patients will be submitted to the PMC within three months of completing the study enrollment. This protocol will be subject to periodic internal audits based on risk or as recommended by the PMC.

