16.2 SAE REPORTING

The following SAE reporting requirements are in addition to those detailed in section [8.4.2](#). Information about all serious adverse events will be collected and recorded. To ensure patient safety, each serious adverse event must be reported to the PI and to the sponsor expeditiously. Moffitt Cancer Center and all participating sites will report SAEs by completing an SAE report in OnCore, the electronic data capture system. The SAE must be reported by email ([contact]) to the External Site Coordination (ESC) office within 2 working days. If applicable, the site should also follow protocol guidelines for additional reporting to government agencies.

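### The 8.5 halting rule counts grade 3 events whether serious or not, but only SAEs have a deadline for reaching the lead PI or the coordinating office, and no one is explicitly assigned the count

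*Combined protocol and SAP*

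**What the plan says.** **The trigger (8.5).** Dosing is halted at three grade 3 AEs judged *probably related*, serious or not. Then: "The study sponsor and investigators will be notified immediately when the third grade 3 event is reported". Enrolment stops and the Protocol Monitoring Committee (PMC) holds an ad hoc meeting.

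**The reporting routes.**
- 8.4.1: "Only SAEs will be reported to the PI and Regeneron Pharmaceuticals, Inc". For non-serious events the same section says that "only Grade 3 toxicities deemed possibly, probably or definitely related to the study treatment will be reported on the appropriate CRFs/SAE reporting forms", with no time limit.
- 8.4.2: "All SAEs will be reported to the PI and Regeneron Pharmaceuticals, Inc. within 24 hours after identification".
- 16.2: SAEs go by email "to the External Site Coordination (ESC) office within 2 working days".
- 7.8: "Hypersensitivity infusion reactions should be reported to the site principal investigator and Regeneron Pharmaceuticals, Inc. within 24 hours of the event regardless of grade".

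**The causality scale (8.2.2).** "The degree of certainty about causality will be graded using the categories below". Two categories follow: Related and Not Related.

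**Oversight.** 8.6 places continuous monitoring with each site's own team and provides a monthly call of all sites and a monthly PMC review, plus a report once the first three patients have completed two cycles. It adds: "The data and safety plan will define criteria for stopping the trial according to rules set forth by this protocol". Section 15.1 gives the Protocol Chair a general duty to monitor the trial and review safety reports. Section 9 places the data in one database, OnCore, and asks for timely data without setting a time.

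**The concern.** The promise of immediate notice in 8.5 starts when the third event is reported. For a non-serious event, nothing in the text says how soon that report must be made to anyone who sees all the sites. Each of three sites could hold one such event and each be fully compliant, while the trial has already met its halting condition.

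The trigger is also hard to apply consistently. 8.5 counts *probably related* events, 8.4.1 uses possibly, probably and definitely, and 8.2.2 offers only two levels. Two sites could classify the same event differently for the count.

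This is the only numerical study-level safety trigger, in a population for which section 2.1 says that the drug's safety is unknown. Section 6.1.8 generally already holds the affected patient's dosing. What is at stake is continued dosing of the other patients and continued enrolment.

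**Working it through.** **1. Which counted events have a clock.** I read *the PI* in 8.4 as the lead PI, because the protocol uses a separate term for the site PI.

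| Counted grade 3 event | Deadline | Recipient |
|---|---|---|
| SAE | 24 hours (8.4.2) | PI, drug supplier |
| SAE | 2 working days (16.2) | External Site Coordination (ESC) office |
| Hypersensitivity infusion reaction, non-serious | 24 hours (7.8) | site PI, drug supplier |
| Any other non-serious event | none | CRF/SAE form (8.4.1) |

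By contrast, protocol deviations have a 7-working-day limit (14.3).

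**2. The plan's own computed figure.** The halting rule has no stated operating characteristics. The only computed design figure is in 10.5. For 27 patients, success at 7 or more responses gives an exact one-sided alpha of 0.0986 at a response rate of 0.15 and power of 0.838 at 0.33. Both match the plan. The reporting route does not enter this test.

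**3. Chance that the rule fires at all.** The documents give no rate of related grade 3 events, so the rate r is an assumption (at most one counted event per patient, independent). P(at least 3 of 27):

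| r | 5% | 10% | 15% | 20% |
|---|---|---|---|---|
| P(fires) | 15% | 52% | 79% | 93% |

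This is the chance of firing, not of firing late.

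**4. When the third event falls.** P(N = n) = C(n−1, 2) r³ (1−r)^(n−3), restricted to n ≤ 27, with the event counted at enrolment. Accrual is 27/12 = 2.25 patients per month (10.4.2). Given firing, the mean is patient 15.7 (month 7.0) at r = 15%, and patient 13.6 (month 6.0) at r = 20%. About 15.75 and 13.5 patients, respectively, are enrolled by then.

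**5. Illustrative cost if recognition waits for a monthly review.** The average wait is 15 days if the call and the PMC meeting coincide, and 7.5 days if they are evenly spaced (assumed).
- Further enrolments = days/30.4 × 2.25: 0.56 at 7.5 days, 1.11 at 15 days, 2.22 at 30 days. With a 24-hour report it would be 0.07.
- Doses to other patients = (enrolled − 3) × fraction on treatment × days/21. With half on treatment (assumed):
  - Month 6: 10.5 × 0.5 × 7.5/21 = 1.9; at 15 days, 3.8.
  - Month 7: 12.75 × 0.5 × 7.5/21 = 2.3; at 15 days, 4.6.
- With everyone else on treatment and a 30-day wait: 15.0 (month 6) and 18.2 (month 7).

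**6. How often firing would be late.** Let s be the share of counted events that are serious (assumed). The third event is non-serious with probability 1 − s: 70%, 50%, 30% or 10% for s = 0.3, 0.5, 0.7 or 0.9. A simulation under the same assumptions, with monthly reviews catching earlier non-serious events, gives about 72%, 53%, 33% and 11% when the two reviews coincide, and about 70%, 50%, 30% and 10% when they are evenly spaced. Averaged over all firings, the wait is about 11, 8, 5 and 2 days, or 5, 4, 2 and 1 days.

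**The case against.** **The strongest case against.** The Protocol Chair has trial-wide safety duties (15.1), and all sites enter data into OnCore, so someone may see the third event promptly. The data and safety plan cited in 8.6 is not among the documents and may contain a route. Many grade 3 immune-related events could be deemed serious as important medical events (8.1.2): Appendix 1 recommends oral steroids for a grade 3 rash, and an investigator could start the 24-hour clock on that basis. The drug is already approved for this cancer, the affected patient is generally held, and the central estimates are small.

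**What stands of it.** These points reduce the size of the concern but do not close the gap. 15.1 does not mention the 8.5 count, and OnCore entry of AEs has no deadline. The unseen plan might supply a route, but 8.6 has it follow the protocol's rules, so the protocol is the place to settle one. The serious share may well be high, and the delay shrinks accordingly.

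**Stronger readings that a reader might infer.**
- *That the protocol makes the halt wait for a monthly review, or up to 30 days.* It does not. The monthly review is the next scheduled cross-site look, not a stated bound. Recognition could be earlier through OnCore, or later because CRF entry has no time limit.
- *That a late halt is near certain because at least one of three events will probably be non-serious.* That probability, 1 − s³, is 97%, 88%, 66% or 27% for the same values of s, but it does not measure delay. An earlier non-serious event will normally have passed a monthly review before the third occurs. The relevant figure is close to 1 − s.
- *That no one oversees safety across sites.* The Protocol Chair does. What is missing is an explicit assignment of the count.

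**Conclusion.** The concern holds in a limited form. The trigger in 8.5 and the reporting rules in 8.4.1, 8.4.2 and 16.2 do not match: a non-serious counted event has no deadline for reaching the lead PI or the ESC office, the count is not explicitly assigned, and the causality scale lacks the category being counted. Following the text exactly can delay or blur the halt. If all three events are SAEs, this delay does not arise.

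The illustrative cost, if recognition waits for a monthly review, is about 1 further enrolment and 2 to 5 doses to other patients. The event rate, serious share, fraction on treatment and review spacing are all assumptions, and the doses measure delay, not harm. Nothing here touches alpha, power or the primary analysis. The change is worth making because it is cheap and protects the one numerical safety trigger; the gap does not make the design unsound.

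**What to change.** 1. **8.4.1:** report SAEs, and every grade 3 or higher AE judged possibly, probably or definitely related, whether serious or not, to the lead PI and the ESC office within 24 hours of identification, through the existing OnCore and email route.
2. **8.2.2:** replace the two levels with not related, possibly, probably and definitely related, and state that the last three together mean Related. This is preferable to counting all Related events in 8.5: Related under 8.2.2 can rest on timing alone, so the rule would fire more readily. For scale, if the counted rate rose from 15% to 20%, firing would rise from 79% to 93%.
3. **8.5:** count grade 3 or higher AEs judged probably or definitely related. State that the lead PI (Protocol Chair) with the ESC office keeps the running cross-site count and, at the third event, notifies the PMC and all sites and suspends registration and dosing. The ESC office already registers every subject (16.3), so it can stop enrolment directly.

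**Cost:** a few sentences, expedited entry of a small number of non-serious events, and a slightly more readily triggered rule, because grade 4 and 5 events and *definitely related* events are now counted explicitly.

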8.6 SAFETY OVERSIGHT

Serious Adverse Events: Serious Adverse Events (SAEs) from this protocol will be reported concurrently to the IRB (per IRB reporting guidelines), the study sponsor via submission through The Online Collaborative Research Environment (OnCore). SAEs will also be reported to Regeneron Pharmaceuticals, Inc.

Protocol Monitoring Committee (PMC):

The PMC meets monthly and reviews accrual, patterns and frequencies of all adverse events, protocol violations and when applicable, internal audit results.

The data and safety plan will define criteria for stopping the trial according to rules set forth by this protocol. This trial will be continuously monitored by the site PI and the research team at each participating institution. All participating sites will have a monthly teleconference calls to monitor any safety concerns. Safety and monitoring reports will be submitted to the PMC after completing the first 2 cycles after the enrollment of initial 3 patients or more frequently if requested by the PMC. No additional interim analyses will be conducted. A final safety and monitoring report including all 27 patients will be submitted to the PMC within three months of completing the study enrollment. This protocol will be subject to periodic internal audits based on risk or as recommended by the PMC.

9 CLINICAL MONITORING

Data will be captured in OnCore, Moffitt's electronic Clinical Trials Database. For each participant enrolled, the electronic CRF must be completed by the assigned data manager or other authorized study staff. Any paper forms should be typed or filled out indelible ink and must be legible. Errors should be crossed out but not obliterated, the correction inserted, and the change initialed and dated by the investigator or his/her authorized delegate. This also applies to records for those patients who fail to complete the study. If a patient stops dosing or terminates from the study, the dates and reasons must be noted on the CRF. If a patient terminates from the study because of toxicity, thorough efforts should be made to clearly document the outcome. Regulatory documents and case report forms will be monitored internally according to Moffitt Cancer Center Monitoring Policies. Monitoring will be performed regularly by the MCC Clinical Monitoring Core for accuracy, completeness, and source verification of data entry, validation of appropriate informed consent process, reporting of SAEs, and adherence to the protocol, Good Clinical Practice (GCP) guidelines, and applicable regulatory requirements. The investigator should ensure the accuracy, completeness, legibility, and timeliness of the data reported to the Protocol Monitoring Committee.

10 STATISTICAL CONSIDERATIONS

10.1 STATISTICAL AND ANALYTICAL PLANS

This is a single arm phase II clinical trial assessing the overall response rate of Cemiplimab-rwlc in immunocompromised patients with unresectable local recurrence and/or metastatic CSCC.

10.2 STATISTICAL HYPOTHESES

We hypothesize that the response rate to Cemiplimab-rwlc in immunocompromised patients is clinically meaningful as observed in immunocompetent patients.

10.3 ANALYSIS DATASETS

The response, toxicity, and survival data obtained from immunocompromised patients treated with

Cemiplimab-rwlc will be analyzed.

10.4 DESCRIPTION OF STATISTICAL METHODS

10.4.1 GENERAL APPROACH

The primary analysis of efficacy is based a one-sided exact test.

10.4.2 ANALYSIS OF THE PRIMARY EFFICACY ENDPOINT(S)

The primary endpoint for efficacy analyses is the ORR. All response assessments are done by RECIST 1.1 analysis of radiologic scans. In some patients, response assessments include photos and radiologic scans and evaluated by composite efficacy criteria (see Appendix 2). Clinical lesions will only be considered measurable when they are superficial (eg, skin nodules and palpable lymph nodes) and ≥ 10 mm (≥ 1 cm) diameter as assessed using calipers (e.g., skin nodules). In the case of skin lesions, documentation by color photography, including a ruler to estimate the size of the lesion, is recommended. Patients who are deemed as not evaluable according to RECIST 1.1 or inevaluable by the composite efficacy criteria will be considered as not reaching PR/CR for ORR.

We expect to complete the accrual in 12 months and the total study duration will be 24 months.

10.4.3 ANALYSIS OF THE SECONDARY ENDPOINT(S)

The secondary analyses of efficacy as measured by PFS and OS will be summarized by median and its 95% confidence interval using the Kaplan-Meier method.

10.4.4 SAFETY ANALYSES

Safety observations and measurements including drug exposure, AEs, laboratory data, vital signs, and Eastern Cooperative Oncology Group (ECOG) performance status will be summarized and presented in tables and listings.

10.5 SAMPLE SIZE

A sample size of 27 achieves 83.8% power to detect a difference ($P_1 - P_0$) of 0.18 using a one-sided exact test with a target significance level of 0.1000. The actual significance level achieved by this test is 0.0986. These results assume that the population proportion under the null hypothesis (P_0) is 0.15.

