While immunocompromised patients have the most need for novel treatment options, they are often excluded in clinical trials. Recently, the programmed cell death-1 (PD-1)/programmed cell death-ligand 1 (PD-L1) axis was determined to play an important role as immune checkpoint. PD-1 is one of the clinically significant checkpoint molecules that has been shown to suppress T-cell function upon binding to its ligands, PD-L1 and PD-L2, which are expressed on tumor cells in both preclinical models and clinical settings of cancer patients undergoing immunotherapy.^{9,10} In addition to promising efficacy, PD-1 and PD-L1 inhibitors are overall safe and well tolerated in a subset of immunocompromised patients such as patients with HIV infection, and additional studies are currently ongoing.^{11,12} Immunotherapy targeting PD-1 has become a promising therapeutic option in management of CSCC.⁴ Cemiplimab-rwlc is one of the PD-1 inhibitors with the most efficacy and safety data in management of unresectable locally advanced or metastatic CSCC.⁴ With Cemiplimab-rwlc as a monotherapy in patients with metastatic CSCC, overall complete response rate is 7% and partial response rate is 41%. It also has a very favorable toxicity profile. Based on these efficacy and safety data, Cemiplimab-rwlc is now FDA approved for the treatment of patients with metastatic CSCC or locally advanced CSCC who are not amenable to curative surgery or curative radiation.¹³ However, immunocompromised patients were excluded in the Cemiplimab-rwlc trial, and the safety and efficacy of Cemiplimab-rwlc is unknown in this patient population with the most limited treatment options.

Even though it is counter intuitive to use immunotherapeutic approaches to immunocompromised patients, the full mechanism of how PD-1 inhibitors exerts anti-tumor effects are still unknown. In addition, recent data suggest that tumors with high tumor mutation burden respond better to PD-1 inhibitors because of increased presence of neoantigens.^{14,15} Chung, et al. evaluated 1,300 mucosal head and neck SCC, 2,386 lung SCC, and 289 CSCC for tumor mutation burden and found CSCC has the highest number of mutations per megabase among the squamous cell carcinomas from various organ sites.¹⁶ Therefore, it is important to evaluate the efficacy and toxicity of Cemiplimab-rwlc in immunocompromised CSCC patients.

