2.2 RATIONALE

It suggests that CSCC is expected to be extremely sensitive to PD-1 inhibiting agents. However, there is no efficacy data in any immunocompromised population due to exclusion of these patients in clinical trials using PD-1 inhibitors. This population specific data are required to fulfill the unmet need.

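### Does testing ORR against 15% leave the hypothesis in section 10.2, which refers to immunocompetent patients, untested?

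*Combined protocol and SAP*

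**What the plan says.** - **Section 10.2** gives the only hypothesis, without a number: "We hypothesize that the response rate to Cemiplimab-rwlc in immunocompromised patients is clinically meaningful as observed in immunocompetent patients".
- **Section 10.4.1** names one efficacy test: "The primary analysis of efficacy is based a one-sided exact test".
- **Section 10.5** sizes the trial: "A sample size of 27 achieves 83.8% power to detect a difference" of 0.18 at a target one-sided level of 0.10, with an actual level of 0.0986. It adds: "These results assume that the population proportion under the null hypothesis" is 0.15. The alternative is therefore 0.15 + 0.18 = 0.33. No source is given for either rate.
- **Section 10.4.2** makes ORR primary and counts inevaluable patients as non-responders, so the denominator stays at 27. It gives no interval for ORR and no rule for reading ORR against another population.
- **Section 2.1** supplies the only response rates for the drug, in metastatic CSCC: "overall complete response rate is 7% and partial response rate is 41" (per cent). It then says: "However, immunocompromised patients were excluded in the Cemiplimab-rwlc trial".
- **Section 3** states the primary objective as determining the response rate, with no comparison.

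**The concern.** The hypothesis mentions immunocompetent patients, but the test does not involve them. If section 10.2 is read as claiming a rate like theirs, the natural yardstick is 48%, and the design alternative of 33% lies 15 points below it. A trial could then be declared positive on data that point to a lower rate than the one hypothesised. A reader might take rejection of 15% as confirming 10.2, when the data support only a rate above 15% and below the one quoted for immunocompetent patients. The plan does not say in advance which statement to make, and 10.5 does not say why exceeding 15% would be meaningful.

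Sections 2.1 and 2.2 also differ in tone. The first says "In addition to promising efficacy, PD-1 and PD-L1 inhibitors are overall safe and well tolerated in a subset of immunocompromised patients", such as those with HIV; the second says "there is no efficacy data in any immunocompromised population due to exclusion of these patients in clinical trials using PD-1 inhibitors". Section 10.5 refers to neither.

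**Working it through.** **Inputs.** N = 27, null rate 0.15, alternative 0.33, one-sided 0.10 (section 10.5). Benchmark 0.07 + 0.41 = 0.48 (section 2.1; the documents do not print the sum). X is the number of responders, binomial with N = 27.

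**1. The plan's own figures.** The cut-off is the smallest r with P(X ≥ r | 0.15) ≤ 0.10.

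- r = 6: 0.2097, too large.
- r = 7: 0.0986, the stated actual level.
- Power: P(X ≥ 7 | 0.33) = 0.8379, the stated 83.8%.

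Success is therefore 7 or more of 27, and section 10.5 is arithmetically right.

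**2. Positive results set against 48%.** The upper tail is P(X ≥ x | 0.15) and the lower tail is P(X ≤ x | 0.48). The interval is the two-sided 95% Clopper-Pearson interval.

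| Responders | ORR | p against 15% | p below 48% | 95% CI |
|---|---|---|---|---|
| 7 | 25.9% | 0.0986 | 0.0163 | 11.1% to 46.3% |
| 8 | 29.6% | 0.0398 | 0.0415 | 13.8% to 50.2% |
| 9 | 33.3% | 0.0138 | 0.0905 | 16.5% to 54.0% |
| 10 | 37.0% | 0.0042 | 0.1718 | 19.4% to 57.6% |

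At one-sided 0.10, exactly 7, 8 and 9 are both above 15% and below 48%. By the 95% interval, only 7 excludes 48%.

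**3. How often this would happen.** P(7 ≤ X ≤ 9) is 41.6% at a true rate of 25%, 44.2% at 33%, 26.7% at 40% and 8.5% at 48%. At 33% this is 0.4416 / 0.8379 = 52.7% of all positive results. Counting only 7 responders, which the 95% interval supports, the probability at 33% is 12.6%.

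**4. How firm the band is.** The calculation treats 48% as known without error, but the documents give no denominator.

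- With a fixed benchmark of 47%, the lower tail is 0.0210, 0.0515 and 0.1086 for 7, 8 and 9, so 9 drops out. The probability at 33% then falls to 28.1% (7 or 8 responders).
- With assumed benchmark denominators of 50, 100 and 200 at 48%, a one-sided Fisher test for 9 of 27 gives 0.159, 0.126 and 0.109. For 8 of 27 it gives 0.093, 0.067 and 0.054. Again 9 drops out and 8 stays.
- Over an assumed fixed benchmark from 43% to 53%, the band runs from 7 alone (12.6% at a true 33%) to 7 to 10 (58.4%).

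**5. The wording.** In section 10.2 the predicate is that the rate is clinically meaningful; the reference to immunocompetent patients qualifies it. The plain reading is that the response will be meaningful, as it was in them. That claims neither equality with nor closeness to 48%. The design fits this reading: an alternative of 33% would be an odd choice for a trial meant to show parity with 48%, and the objective in section 3 is to determine a rate.

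**The case for a change.** The strongest case for a change does not depend on 48%. Under either reading of section 10.2 something is missing. If it means parity, the test does not address it. If it means only meaningful, there is no threshold, and section 10.5 never says why 15% marks the floor. Section 10.4.2 plans no interval for ORR, although section 10.4.3 plans 95% intervals for PFS and OS. The lack of population-specific data is the stated reason for the trial, so readers will want to set the result beside the immunocompetent rate. Wording fixed before the data are seen would prevent a convenient reading afterwards, at the cost of a few sentences.

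Part of this stands. The hypothesis carries no number, 15% and 33% carry no reason, and rejecting 15% does not show similarity to immunocompetent patients. But these are gaps in explanation. An analyst reporting 27 patients would give the ORR with an exact interval as a matter of course, and that interval shows directly whether 48% is excluded.

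A formal rule using a p-value against 48% would do harm. It would add a second decision rule based on an external figure of unknown precision, for metastatic disease only, in a trial that also enrols unresectable locally recurrent disease. At 8 or 9 responders it would report a rate below 48% beside a 95% interval that contains 48%. It would also report a positive result as below 48% with probability 8.5% when the true rate is 48%.

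The contrast between sections 2.1 and 2.2 adds little. The HIV sentence chiefly concerns tolerability and supplies no response rate for the design.

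**Conclusion.** No change to the plan follows. The test is a standard single-arm design against a low-activity null; its level (0.0986) and power (83.8%) are correct, and nothing in the documents shows 15% to be the wrong null. A positive result supports the conclusion that ORR exceeds 15%, and the plan does not say that it supports more.

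The apparent contradiction rests on three assumptions: that section 10.2 asserts parity, that 48% is the right comparator for the whole population, and that 48% is known exactly. The wording and the design tell against the first, and the documents do not support the other two. Without them, the 44.2% probability at a true 33% falls to 28.1% if 9 responders drop out, or to 12.6% if a 95% interval is the criterion.

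The residue is missing detail: a hypothesis stated without its number and two design rates without a stated reason. Filling it in would alter neither N, the test, the cut-off of 7 nor the result. A report that sets the ORR beside the immunocompetent rate should treat that comparison as descriptive.
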